Doubly robust estimation features a dual strategy of outcome regression that also accounts for the likelihood of receiving an exposure or treatment, such as with a PS. Simply using multivariable regression or PS analysis can lead to biased treatment estimates if either model is incorrectly specified. But with doubly robust estimation using both concurrently, only one model must be correctly specified to produce unbiased estimates. Of all the forms of PS analysis (i.e., matching, stratification, weighting, and adjustment), regression that includes the PS as one of the adjusted variables has quantitative evidence as being the top performing PS method. Finally, mixed effects regression further provides a powerful approach to causal inference. This mixed method contains both fixed effects (FE) and random effects (RE) components, with FE having the distinct advantage of controlling even for nonobserved traits by controlling for all time-invariant traits. FE does this by setting each individual subject as his/her own control and thus models within-person effects. Aside from the theoretical advantages, FE has shown quantitative strengths over competing methods. RE was used to control for what FE cannot,

Version Date: 09/26/15 Version Number: 1 Page 8 of 9 namely, time-varying traits at the individual level with repeated observations over time (as students progressed through their medical education). The multilevel aspect was used to account for the hierarchical nature of the data in which medical trainees responded from different medical institutions. Inverse-variance weighted fixed effects (IVWFE) meta-analysis was used to produce a composite estimate across the 25 competency topics.

This triply robust approach can be represented by the following mathematical formula:

$$\Pr(y_{ij} = 1 \mid u_j) = H(x_{ij}\beta + z_{ij}u_j)$$
(1)

for *M* independent clusters conditioned on random effects  $u_j$  for j = 1, ..., M clusters with cluster *j* constituting  $i = 1, ..., n_j$  observations, outcome  $y_{ij}$ , FE covariate  $x_{ij}$ , RE covariate  $z_{ij}$ , and regression coefficient  $\beta$ , all within a logistic regression equation with logistic cumulative distribution function of  $H(\bullet)$ . The PS is utilized as an additional variable in the above model and is represented as

$$e(x_i) = \Pr(z_i = 1 \mid x_i)$$
(2)

in which exposure probability is conditioned on the covariate  $x_i$  observed.

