The competing causal inference methods of instrumental variable and difference in difference analyses were not utilized due to their methodological weaknesses, respectively, of having varying degrees of reliable instrumental variables and having a prevalence of unobserved confounders exerting time-varying effects before and after the exposure/treatment. The above methods of doubly robust PS adjustment in multivariable regression were therefore integrated with multilevel mixed effects to provide a novel triply robust approach to causal inference. Aside from controlling for the likelihood of receiving GCCM education (via the PS) and unobserved time-invariant traits (via FE) and time variant along with intracluster correlation (via RE), this integrative method controlled via regression for age, gender, race, prior nutrition education, special diet, school year, intended specialty, and medical school. This multilevel approach has a Bernoulli conditional distribution of the response given the random effects and logistic cumulative distribution function for the success probability.

All results are reported as fully adjusted ORs. ORs rather than relative risks were calculated due to the complex data source described above and due to the rare disease assumption. Statistical significance was set at a two-tailed *p* value < 0.05. ML analysis was performed in R 3.3.2 (The R Foundation for Statistical Computing, Vienna, Austria). Statistical analysis was performed in STATA 14.2 (STATACorp, College Station, Texas, United States of America). Ethics approval was obtained through the Institutional Review Board (IRB) of Tulane University.

Version Date: 09/26/15 Version Number: 1 Page 9 of 9

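### The SAP claims a doubly and triply robust analysis of medical trainees, but a propensity score added as a covariate to a logistic mixed model does not guarantee an unbiased odds ratio when only the propensity score is right

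*Combined protocol and SAP*

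**What the plan says.** All the relevant text is in the SAP, under Machine Learning and Statistical Analysis.

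- The property claimed: "But with doubly robust estimation using both concurrently, only one model must be correctly specified to produce unbiased estimates".
- The PS method chosen, over matching, stratification and weighting: "regression that includes the PS as one of the adjusted variables has quantitative evidence as being the top performing PS method".
- The implementation, after logistic mixed model (1): "The PS is utilized as an additional variable in the above model". Equation (2) defines the PS on the probability scale, e(x) = Pr(z = 1 | x).
- The outcome regression also "controlled via regression for age, gender, race, prior nutrition education, special diet, school year, intended specialty, and medical school". No functional forms are given, and the PS model's own covariates and diagnostics are not listed.
- The label: PS adjustment is "integrated with multilevel mixed effects to provide a novel triply robust approach to causal inference".

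The SAP describes no weighting, augmentation, inverse-PS term or standardisation step. It says that results are reported as fully adjusted ORs.

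**The concern.** Double robustness is a property of particular estimators. They combine outcome predictions with inverse-probability weights, so that an error in one working model is corrected by the other. Augmented inverse-probability weighting (AIPW) and inverse-probability-weighted regression adjustment are examples. A PS entered as a covariate is part of the outcome model. There is then one likelihood, and if its form is wrong nothing outside it corrects the treatment coefficient.

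The same holds for the claimed third layer. Random effects in equation (1) represent clustering and repeated responses. They are not an alternative working model that could be right when the other two are wrong.

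This matters because protocol section 3 describes the trainee classes as voluntary, so self-selection is the main threat to the comparison, and the SAP claims causal inference. Readers are told that a correct PS alone is enough. They would trust the published OR more than the method allows, and would not know whom it describes.

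**Working it through.** The SAP gives no numerical figure for this point to reproduce. Its one design figure, 263 cases for an OR of 1.50, does not bear on it. The check is of the estimator's property, in large simulated samples. Every parameter below is an assumption, because the documents give none. Random effects were left out to isolate the PS step.

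**Model as in the SAP.** Fit logit Pr(Y=1) = a + bZ + cx + d·e(x), with the true e(x) supplied, and report exp(b).

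**Comparator.** AIPW with the same true PS and the same wrong outcome form: the mean under exposure z is the average of q_z + 1(Z=z)(Y − q_z)/Pr(Z=z | x), where q_z is the prediction from a logistic model in Z and linear x.

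**Common-effect scenario.** x is standard normal; logit e(x) = −0.5 + 1.2x; true logit Pr(Y=1) = −1 + 1.5(x² − 1) + ln(OR)·Z. The fitted outcome model is wrong because it omits x². Samples had 1 to 4 million subjects; ranges show the spread between runs.

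| True conditional OR | True marginal OR | Linear x, no PS | Linear x plus true PS | AIPW marginal OR |
|---|---|---|---|---|
| 1.00 | 1.00 | 1.21 | 1.00 | 1.00 |
| 1.50 | 1.29 | 1.54 | 1.34–1.35 | 1.28 |
| 3.00 | 2.05 | 2.50 | 2.34–2.36 | 2.05 |

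On the log scale the estimate keeps ln 1.35/ln 1.50 = 0.300/0.405 = 0.74 of the conditional effect, and ln 2.36/ln 3.00 = 0.859/1.099 = 0.78. It equals neither the conditional nor the whole-population marginal OR. The no-PS value of 1.54 lies near 1.50 only because upward confounding, visible as 1.21 under the null, offsets the attenuation.

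**Why the null survives.** If treatment affects nobody, set b = 0, so the fitted mean m depends on x only. The score for Z is then E[Z(Y − m)] = E[e(x)(Y − m)]. The score equation for the e(x) term sets this to zero, so b = 0 solves the system. The argument needs e(x) on the probability scale. In this scenario the logit-scale PS is collinear with x and gives 1.21 under the null.

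**Coverage in the same scenario** (500 replicates each, true conditional OR 1.50, nominal 95% interval): 90% at n = 1,000, 72% at 5,000 and 46% at 10,000. The last is the track 1 target in protocol section 2.

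**Other common-effect scenarios, true conditional OR 1.50.** Estimates were 1.37, 1.45, 1.50 and 1.51, so the bias depends on the scenario. With the outcome model right and the PS wrong, estimates were 1.495 to 1.523. The protection therefore runs one way, from the outcome model.

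**Heterogeneous effect.** logit e(x) = −0.8 + 1.2x; true logit Pr(Y=1) = −0.3 + 0.5x + Z(ln 1.5 − 0.6x).

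| Quantity | Risk difference | OR |
|---|---|---|
| True, whole population | 0.097 | 1.48 |
| True, weighted by e(1 − e) | 0.0625 | 1.28 |
| True, class-takers | 0.009 | – |
| Linear x plus true PS | 0.063 | 1.30 |

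The PS-covariate model lands on the overlap-weighted effect.

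**The case against.** The best defence is that covariate adjustment for a correct PS does real work. It does. Under a strict null, two further scenarios gave 1.70 and 2.65 from the wrong outcome model without the PS, and about 1.00 with it. Since the null holds, the common-effect gap mainly reflects non-collapsibility of the OR under a wrong outcome form, not confounding left in place. This part stands, but it falls short of the unbiasedness that the SAP asserts. Nor can the label be read as loose usage, because the SAP spells out the one-correct-model guarantee.

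Three stronger readings are tempting and are not supported.

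- A reader might infer that a correct PS gives no protection at all. The null results contradict that.
- A reader might take the heterogeneous case as showing an effect 36% too small (1 − 0.062/0.097). That scores the model against a whole-population effect that the SAP never names. Against the class-takers' effect of 0.009 the same estimate is far too large. The case is also extreme, since benefit turns to harm above x = 0.405/0.6 ≈ 0.68. With an interaction of −0.2 in place of −0.6 the figures were 0.085 against 0.096. What it exposes is an unstated target.
- A reader might extend the point to every non-randomised track. The SAP text concerns medical trainees: school year, intended specialty, medical school and 25 competency topics. Nothing applies this model to the community or employee tracks.

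A fair caution also applies to the remedy. AIPW handles measured confounders only, does not carry over the within-person component on which the SAP relies for unobserved stable traits, and changes a conditional OR into a marginal effect.

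**Conclusion.** The point holds for the medical-trainee analysis. Equation (1) with the PS as a covariate is not doubly robust, and random effects do not make it triply robust. With a correct PS and a wrong outcome model it keeps a strict null and removes much measured confounding, but it does not guarantee an unbiased adjusted OR when there is an effect. In the assumed scenario 1.50 became about 1.35 and 3.00 about 2.36; in other assumed scenarios the bias was negligible. With heterogeneous effects the estimate is roughly overlap-weighted.

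That the property is missing follows from the form of the estimator and needs no assumed parameters. The sizes rest wholly on assumed parameters, a true PS on the probability scale and no random effects. The bias in this study cannot be worked out from the documents. The claims should be corrected, because the causal interpretation leans on them.

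**What to change.** 1. Delete the triply robust label and the one-correct-model statement as applied to equation (1). State that the validity of the adjusted OR depends on the outcome model.
2. State the target effect: marginal or conditional, and in which population.
3. Add an estimator that has the property, either AIPW or inverse-probability-weighted regression adjustment. Use the same covariates with school in both models, and standard errors that respect repeated responses within respondent and clustering by institution. Include an overlap check and label the result as a marginal effect.
4. Report it alongside equation (1), not in its place, since the two answer different questions and rest on different assumptions.

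The cost is a little more analysis, and wider intervals if some PS values are near 0 or 1. Items 1 and 2 are changes of text only.

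### The SAP claims own-control fixed effects and time-varying control by random effects, but equation (1) is an ordinary mixed logistic model that gives neither

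*Combined protocol and SAP*

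**What the plan says.** The point concerns the SAP section on machine learning and statistical analysis, as it applies to the medical-professionals track.

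- **Claim for FE.** The section describes the mixed model "with FE having the distinct advantage of controlling even for nonobserved traits by controlling for all time-invariant traits", and gives the mechanism: "FE does this by setting each individual subject as his/her own control and thus models within-person effects".
- **Claim for RE.** RE is said to control what FE cannot, namely "time-varying traits at the individual level with repeated observations over time". The covariate paragraph later repeats both claims: "unobserved time-invariant traits (via FE) and time variant along with intracluster correlation (via RE".
- **Model.** Equation (1) is Pr(y_ij = 1 | u_j) = H(x_ij β + z_ij u_j), for "independent clusters conditioned on random effects". The text adds: "This multilevel approach has a Bernoulli conditional distribution of the response given the random effects".
- **Level.** The only level named is the institution: "The multilevel aspect was used to account for the hierarchical nature of the data in which medical trainees responded from different medical institutions". Medical school is also listed among the regression covariates.
- **Propensity score.** Equation (2) is a score "in which exposure probability is conditioned on the covariate" that was observed.

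The same section says the regression was done for causal inference and names fixed effects as one of two main supports. Protocol section 3 makes track 1 attendance voluntary.

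**The concern.** The SAP uses the term fixed effects in two senses. In a mixed model it means coefficients common to all subjects. In panel analysis it means a separate effect for each person, removed by conditioning or differencing, so that only within-person change informs the estimate. Only the second controls unobserved stable traits. The SAP claims that property, but the model it writes down is of the first kind.

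People who choose a cooking and nutrition class may differ beforehand in stable ways that no covariate captures, such as interest in nutrition. A reader who accepts the FE claim would take the reported OR as free of such selection. Pooling over 25 competency topics would not help: it narrows the interval around any bias the topics share.

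**Working it through.** **1. Text against model**

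| Claimed | What equations (1) and (2) contain |
|---|---|
| Each subject is his or her own control | x_ij, labelled the FE covariate, has one common β; no fixed person intercept, conditional likelihood or person-mean exposure |
| All unobserved stable traits removed | u_j is random and assumed independent of attendance, whether j is the person or the institution |
| Time-varying traits controlled by RE | A random intercept is constant over time; a random slope is still assumed independent of attendance |
| Selection handled by the propensity score | The score conditions on observed covariates only |

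The eight listed regression covariates include no person indicator. They do include gender and race; where these are constant within a person, their coefficients could not be estimated beside person fixed effects.

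**2. Illustration of size**

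The only input from the SAP is the yardstick OR of 1.50 in its Power Analysis. The 263 cases stated there play no part. Everything else is assumed:

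- One topic, a start and an end survey, exposure counted at the end survey, true OR 1.00.
- Unmeasured stable trait u ~ N(0,1); other stable variation v ~ N(0, s²), unrelated to attendance.
- P(class) = expit(−0.5 + g·u).
- P(positive answer) = expit(b0 + g·u + v + 0.2·wave), with b0 = 0 and no class effect.
- g = ln 1.5 or ln 2.
- Latent ICC = (g² + s²) / (g² + s² + π²/3). The lowest ICC has s² = 0: (ln 1.5)² = 0.164 gives 0.164/(0.164 + 3.290) = 0.05, and (ln 2)² = 0.480 gives 0.13.

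The values below are large-sample limits by Gauss-Hermite quadrature, so no sample size is assumed. There is no measured proxy for the trait.

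| Latent ICC | Person random intercept, trait OR 1.5 | Trait OR 2 | Conditional logit, both | Share whose answer changes |
|---|---|---|---|---|
| 0.05 (0.13 for OR 2) | 1.165 | 1.485 | 1.00 | 48% (45%) |
| 0.30 | 1.13 | 1.41 | 1.00 | 39% |
| 0.55 | 1.10 | 1.30 | 1.00 | 30% |
| 0.75 | 1.07 | 1.21 | 1.00 | 22% |

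- **j as institution.** With no person term, the ORs agree to within 0.01.
- **Lower baseline.** With b0 = −1.5, the ORs move by at most 0.02.
- **Simulation check.** A Monte Carlo run (4 × 400,000 persons) at the lowest ICC, 0.55 and 0.75 gave 1.168/1.098/1.065 and 1.487/1.293/1.219. Conditional logit gave 0.995–1.007.

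**3. Against the design OR**

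ln 1.50 = 0.405. For trait OR 1.5, ln 1.073/0.405 = 17% and ln 1.165/0.405 = 38%. For trait OR 2, ln 1.213/0.405 = 48% and ln 1.485/0.405 = 98%.

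**4. With a measured proxy and its propensity score (ICC 0.55)**

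| Proxy–trait correlation | Trait OR 1.5 | Trait OR 2 |
|---|---|---|
| 0.5 | 1.075 | 1.22 |
| 0.7 | 1.05 | 1.15 |
| 0.9 | 1.02 | 1.055 |

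These are 5–18% and 13–49% of ln 1.50.

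**5. Other settings**

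A simulation with exposure chosen at each wave and trait effects of 0.5 or 1.0 on the log-odds scale gave null ORs of 1.26–2.06 for the person random intercept with propensity score, against 0.97–1.02 within person. With no link between trait and exposure, all three estimators compared (pooled, random intercept, within person) were close to 1.

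**6. Time-varying confounding**

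If the trait acts on the answer only at the end survey, the conditional OR is itself about 1.17 or 1.49–1.52. No estimator discussed here removes that.

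**The case against.** - **The model is not fully itemised.** The contents of x_ij and z_ij are not listed, the formula is offered as a representation, and FE control is named separately from the covariates. Person effects might have been fitted without being described. This stands as a reason to ask what was fitted. It does not support the claim as written: no person term or conditional likelihood is specified, and gender and race are listed as adjusted.
- **The no-proxy sizes are for a barer model than the SAP's.** The SAP adjusts for eight covariates and a propensity score, among them prior nutrition education, special diet and intended specialty. This stands. The proxy values belong beside the no-proxy ones, and a weaker trait (OR 1.2) gives only 1.015–1.033 without a proxy, 4–8% of ln 1.50.
- **Two surveys is the short case.** Protocol sections 1 and 2 plan repeated surveys over years. On the person-intercept reading at ICC 0.55, two surveys before and two after exposure lower 1.10 to 1.07 and 1.30 to 1.21; four and four give 1.045 and 1.13. The bias shrinks but stays. More surveys do not help if j is the institution or if only one survey precedes exposure.
- **No result is shown to be wrong.** This is true. The defect is a causal property attributed to the OR that the written model does not deliver.

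**Conclusion.** The concern holds. The claim that FE removes all unobserved stable traits is not supported by equation (1), whether j is the person or the institution. The claim that RE controls time-varying traits is wrong on either reading. This follows from the text and needs no assumed numbers.

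The size of any bias is unknown. It is nil if attendance is unrelated to unmeasured stable traits. Under the assumed trait strengths it ranges from about 1.01 with a close proxy to 1.485 with none, at a true OR of 1.00. No false-positive rate is quoted, because the documents give no basis for one.

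The fault must be fixed because the SAP rests its causal reading partly on these claims. It concerns the voluntary medical-professionals track, not the randomised one.

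**What to change.** State what j indexes, what x_ij and z_ij contain, and whether u_j is an intercept or includes slopes. Use medical school once, as covariate or as level. Then do one of the following.

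**(a) Withdraw.** Remove the claims that FE controls unobserved stable traits and that RE controls time-varying ones. Describe the OR as adjusted for measured covariates only. This changes SAP wording and no analysis.

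**(b) Estimate within person.** Report, at least beside the mixed model, either conditional logistic regression grouped on the dummy ID with a wave term, or the within-person coefficient from a mixed model that adds each person's mean exposure. Withdraw the RE claim here too. The data exist: the start and end surveys of protocol sections 1 and 3, linked by the dummy ID of section 10.

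The costs of (b), under the illustrative settings above, are:

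- Only repeat respondents contribute, and conditional logit uses only those whose answer changes: 45–48% at the lowest ICC, down to 22% at 0.75. These shares halve if half the respondents answer only once.
- Its interval is wider than the mixed model's: 1.35–1.39 times at the lowest ICC, 1.20 at 0.55 and 1.14 at 0.75. If half answer once, these become 1.65–1.70, 1.43 and 1.32.
- Time-varying confounding remains.
- With a start and an end survey, the estimator is close to the difference-in-difference method the SAP rejects. That rationale needs rewording, because own-control FE shares the weakness given for rejecting it.

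The choice between (a) and (b) is the sponsor's.

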CHOP is a prospective observational cohort study with four tracks ([1] medical professionals, [2] community, [3] employee, and [4] randomized controlled trial [RCT]) to allow results to be compared among the subjects in the four tracks. [1] Current and future medical professionals will be trained in classes within their track in how to educate patients about nutrition, and their results for their DACs will be compared to those who receive traditional clinical education. [2] Adults, adolescents, and children 7 years and older will be offered classes in their community track to allow comparison of their DACs and health metrics with those who do not take the classes. [3] Employees and their families who take the GCCM classes as employee wellness programing will have their DAC and health metrics compared to employees who do not take the classes. And finally, [4] subjects with such chronic health conditions as diabetes will be randomized with equal 50% chance to either taking the GCCM classes or receiving medical nutrition therapy (MNT) with a registered dietician (RD).

DAC surveys will take place for the first track at the beginning and end of each academic year. Surveys will take place for the last three tracks at the first and last class for the treatment (GCCM) class group, and the beginning of the study and 2-3 months later for the control groups (those who do not take the classes). The same adult and children surveys will be used across tracks [2]-[4] for adults 18 years and older and children 7-17 respectively. Medical professionals in [1] will have the same survey.

CHOP unites such analyses as diffusion of innovation (DOI), social network, and simulation-based medical education with deliberate practice (SBME-DP) along with rigorous statistical methods to answer these questions and hopefully benefit society. Results will be strengthened by using self regulation survey with Tulane marketing students to better design the DAC survey based on understanding what DACs predict

Version Date: 09/26/15 Version Number: 1 Page 2 of 9 certain nutrition behavior, in addition to comparison to the de-identified National Health and Nutrition Examination Survey (NHANES) for national trends in diet and similar health metrics and behaviors.

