# 3. Procedure

[1] Medical professionals track: An internet link will be distributed to subjects through the list-serves for each class at the beginning and end of each academic year after they have had the opportunity to participate or not in the voluntary GCCM classes. Residents and practicing physicians who identify themselves through the GCCM website will be subsequently offered the survey. Marketing students will be offered an online survey about self-regulation and nutrition through their marketing class to improve the medical professionals survey.

[2] Community, [3] Employee, and [4] RCT tracks: Subjects in the treatment group will receive up to 20 evidence-based classes (50 hours) of cooking and nutrition education that cover the Mediterranean diet, food shopping, cooking, and storage. Subjects in the control groups for [2] and [3] will not receive the classes, and control subjects in [4] will receive MNT. Control subjects in [2] will additionally have the opportunity to receive either healthy food vouchers for 2 months or have nutrition education for their children before they enroll in the classes in order to compare if increased healthy food access and education compared to GCCM classes best prepares them to benefit from nutrition education. DAC surveys will be used at the beginning and end of the classes for the treatment group, and beginning of the study and 2-3 months later for the control group. Health metrics will be assessed from health records for subjects retrospectively 3 years before and 3 years after their treatment or control exposure, once subjects provide release to the study team of their records with appropriate safeguards to protect

Version Date: 09/26/15 Version Number: 1 Page 3 of 9 the safety of their data. Recruitment for [2] will be through GCCM's website, [3] will be through Laitram that promotes the classes to their employees, and [4] through Tulane University Hospital and Clinic (including the Internal Medicine Practice, Uptown Square clinic, Endocrinology clinic, and Metairie Multispecialty clinic) by study staff. Health metrics will be obtained for [2,4] from Tulane University Hospital and Clinic if subjects' information is stored there, from Marathon Health the third party provider of health care for [3], and from non-Tulane health care institutions for [2,4]. Marathon and non-Tulane facility health information release forms will be provided to subjects as needed at the time of informed consent.

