# **Statistical Analysis Plan**

# **Power Analysis**

The required calculated sample size to achieve 80% power and detect an odds ratio (OR) of at least 1.50 with a two-sided test set at 5% was 263 cases.

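### The SAP names no class-series or household clustering; if its trainee model is carried over to tracks 2-4, classmates and relatives are treated as independent

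*Combined protocol and SAP*

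**What the plan says.** **Delivery.** Under Procedure, for tracks 2-4: "Subjects in the treatment group will receive up to 20 evidence-based classes (50 hours" in total). Controls in tracks 2 and 3 do not take the classes; controls in track 4 receive medical nutrition therapy (MNT) with a dietician. Some track 2 controls may first receive food vouchers or nutrition education for their children, and then enrol in the classes.

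**Families.** Section 1 describes the employee track as covering "Employees and their families who take the GCCM classes", and Section 2 sets the lower age limit there at 7. The community track takes adults and children but does not say that households enrol together. The RCT track is adults only.

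**Model.** The SAP gives one model, a mixed-effects logistic regression with a propensity score as covariate. On grouping between people it says: "The multilevel aspect was used to account for the hierarchical nature of the data in which medical trainees responded from different medical institutions". Random effects are also assigned to "time-varying traits at the individual level with repeated observations over time (as students progressed through their medical education"), and the SAP later says the method handles "time variant along with intracluster correlation (via RE") without saying what the cluster is. The adjustment set is "age, gender, race, prior nutrition education, special diet, school year, intended specialty, and medical school". The outcome described is a set of 25 competency topics.

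**Error rate.** "Statistical significance was set at a two-tailed" p value below 0.05. No class size, ICC or design effect appears anywhere.

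**The concern.** People taught together share an instructor, a group and a schedule, so their outcomes after the classes tend to be correlated. In tracks 2-4 this arises mainly in the GCCM group, which makes the design partially nested. Relatives who eat together are a second source of dependence. The SAP's named grouping level covers neither. Formula (1) conditions on independent clusters: if the cluster is the person, classmates and relatives are assumed independent; if it is the institution, the level has no counterpart in these tracks.

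At stake are the stated two-sided 5% level and the width of the confidence intervals, including those of the randomised comparison in track 4. There, randomisation protects against confounding but does not remove correlation created after allocation by shared teaching.

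**Working it through.** **1. The plan's own figure.** The Power Analysis says "The required calculated sample size to achieve 80% power and detect an odds ratio (OR) of at least 1.50" at two-sided 5% was 263 cases. The outcome rate and allocation are not given, so it cannot be reproduced uniquely. A 1:1 comparison of two proportions needs at least 384 per arm at any control rate. The logistic formula (z_a + z_b)² / [p(1-p)·ln(OR)²] = 7.849 / (0.24 × 0.76 × 0.1644) gives 262, but only by choosing p = 0.24. So 263 is not shown to be wrong. No allowance for clustering is described, and the figure is not tied to a track.

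**2. Inputs for the clustering check.**
- From the documents: two-sided 5%; 80% power; equal groups in tracks 2-4 (3,000/3,000; 1,500/1,500; 500 randomised with equal chance).
- Assumed: class size m = 8-20; ICC = 0.01-0.10; equal class sizes; clustering in the GCCM arm only. Because the model uses each person as their own control, the relevant ICC is that of the change.

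**3. Formulas.** Design effect in the class arm: DE = 1 + (m-1)·ICC. Variance factor for a 1:1 contrast with one arm clustered: R = (1 + DE)/2. True type I error of the naive test: 2·[1 - Φ(1.96/√R)]. Power of a correctly sized test planned for 80%: Φ(2.80/√R - 1.96).

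Worked case, m = 12 and ICC = 0.05: DE = 1 + 11 × 0.05 = 1.55; R = 2.55/2 = 1.275; 1.96/√1.275 = 1.736; type I error 0.083.

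| m | ICC | R | Naive SE too small by | True type I error | Power | 500/R |
|---|---|---|---|---|---|---|
| 8 | 0.01 | 1.035 | 2% | 5.4% | 79% | 483 |
| 8 | 0.05 | 1.175 | 8% | 7.1% | 73% | 426 |
| 12 | 0.05 | 1.275 | 11% | 8.3% | 70% | 392 |
| 20 | 0.05 | 1.475 | 18% | 10.7% | 64% | 339 |
| 20 | 0.10 | 1.95 | 28% | 16% | 52% | 256 |

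The last column is the effective size of track 4.

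**4. Households (illustration only; no input is documented).** With households of 2-3 wholly in one group, both groups clustered and ICC 0.10-0.30, DE runs from 1 + 1 × 0.10 = 1.10 to 1 + 2 × 0.30 = 1.60. Type I error is then 6.2% to 12.1%. If pairs are split between class and no-class groups, the variance factor is 1 - ICC, that is 0.90 to 0.70. The naive standard error is then too large, and type I error falls to 3.9% to 1.9%.

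**The case against.** The strongest reply is that the quoted model is a track 1 model. Its institutions, school year, intended specialty and competency topics all belong to trainees. A reader might infer that standard errors in tracks 2-4 will be too small. The documents do not support that, because they state no analysis for those tracks; the finding is conditional on this model being carried over. What stands is that it is the only model given, and that nothing in the plan would bring in class or household.

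A reader might also infer that institution is the only dependence modelled. That is wrong: repeated observations within a person are covered too, and intracluster correlation is mentioned in general terms. Subject fixed effects would also absorb stable similarity between relatives. But class-induced correlation arises after baseline, in the change itself, so these terms do not remove it.

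Three further limits stand:
- Fixed class membership is not stated, and the wording on the number of classes allows attendance to vary.
- The one-arm premise is less secure where track 2 controls later join classes, or where track 4 controls share a dietician. Grouping in both arms moves the factor from R towards DE.
- Family enrolment is explicit only for track 3, is plausible for track 2, and has no stated basis in track 4.

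**Conclusion.** The point holds in conditional form. No track has class series or household named as a cluster, and the one between-person level that is named has no counterpart in tracks 2-4. If the stated model is applied there and ignores class, true type I error would be about 5.4% to 16%, and 8.3% at size 12 and ICC 0.05. This rests on assumed class sizes of 8-20, assumed ICCs of 0.01-0.10, equal groups and clustering in the class arm only. At the low end the effect can be ignored; in the middle of the range it cannot.

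The household part is weaker. It has a documented basis in track 3 and a plausible one in track 2. Its direction depends on whether relatives share exposure or are split between groups, so a claim that household clustering always narrows the intervals would go too far.

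**What to change.** - **Data.** Record class-series ID and household ID at enrolment, and dietician ID in the track 4 control arm. Do this prospectively: surveys carry self-generated dummy IDs and the code key is held separately, so membership may be hard to rebuild later.
- **Model, tracks 2-4.** State the model for these tracks. Use a partially nested model with a class-series random effect in the GCCM group. If class membership is not fixed, use cluster-robust standard errors instead. Track 4 would have 500 × 50% = 250 in the class arm, hence only about 12 to 31 series (250/20 to 250/8), so name a small-sample correction.
- **Households.** Add a household random effect or household-clustered standard errors in track 3, and in track 2 where relatives enrol. This handles both directions of error.
- **Planning.** State the expected class size and an assumed ICC, and show what they do to power in track 4.

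**Cost.** Two or three ID fields, one more model level, and wider intervals. The widening factor is √R: about 2% at R = 1.035, 13% at R = 1.275 and 40% at R = 1.95.
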